Friends/Family in the Abortion Procedure Room (FAIR): Assessing pain level, patient, staff and support person satisfaction with support person in abortion procedure room: A randomized controlled trial

Principle Investigator: [name], MPH Planned Parenthood of Southwest and Central Florida

PROJECT SUMMARY

Having an abortion is a complexly emotional experience for many women. Women with strong social support, from a partner, friend or family member, report better psychological adjustment [1]. During medication abortion, patients reported high satisfaction levels, in part, because of being able to share the experience with another person [2, 3, 4]. During in-clinic abortion, patients report lower levels of anxiety when they have a support person (partner, spouse, friend or family member) in the post-abortion recovery room. Additionally, support persons indicate feeling they can successfully comfort the woman [5]. In the abortion procedure room, doula support has a positive psychological impact on patients and decreases the need for additional clinic support resources [6]. Because doula support in the abortion procedure room and social support in the post-abortion recovery room improves patient experience, it is reasonable to believe that having a support person in the procedure room may also improve patient experience. However, there are no data about the patient, support person, and health care provider's experience and satisfaction with a support person in the abortion procedure room.

This study aims to explore patient, support person, and health care providers' experience and satisfaction with social support in the abortion procedure room. Although some providers do allow a support person in the abortion procedure room, no study has formally examined the effects of this practice.

If this study demonstrates higher patient satisfaction and lower perceptions of pain and anxiety levels in patients who have social support in the in-clinic abortion procedure room, this could change standard procedures in the in-clinic abortion procedure room, allowing for more positive patient experiences.

1. DESCRIPTION OF THE PROJECT

1.1 Rationale and objectives of the study

1.1.1 Rationale

Following elective abortions, patients with strong social support report greater psychological adjustment than those without support [1]. In medication abortions, there is a psychological benefit to both men and women in being able to support one another and share the abortion process together [2].

The contraceptive partner often has similar motives and feelings as the female partner and is interested in being involved in the abortion experience [3, 4]. Following in-clinic abortion, patients report lower levels of anxiety when they have a social support person in the post-abortion recovery room, and support persons indicate feeling they can successfully comfort the patient [5].

In out-patient surgery procedures, patients with strong social support have less anxiety, take lower doses of narcotics, and recover more quickly from operations [7]. Doula support has had a similar impact on patient experience in the abortion procedure room, resulting in less need for additional clinic support resources. No studies, however, have examined the impact of social support on the patient and provider experience in the in-clinic abortion procedure room. Due to the significant positive outcomes of having a support person in the post-abortion recovery room, doula support in the abortion procedure room and social support in out-patient surgical procedures, a more in-depth exploration of the patient, support person, and health care provider's experience and satisfaction with social support in the in-clinic abortion procedure room is advantageous to improving the patient's abortion process. Additionally, some patients have chosen a facility that allows a support person in the room over facilities that do not support this practice.

In this study, we propose a randomized, controlled trial permitting a social support person of the patient's choosing to join the patient in the in-clinic abortion procedure room.

1.1.2 Hypotheses and Objectives

Hypotheses:

Social support in the abortion procedure room will decrease perceived pain and anxiety levels and increase satisfaction for the patient.

- 1. Social support in the procedure room influenced the patient's health outcomes in the following areas:
 - 1. Decreased pain
 - 2. Decreased anxiety
 - 3. Increased patient satisfaction
- 2. The social support person will report that they were able to give effective support to the patient.
- 3. The physician and the nurse will find the support person effective in supporting the patient.

Null Hypothesis:

- 1. Social support in the abortion procedure room will not change patient levels of perceived pain, anxiety, or satisfaction.
- 2. The social support person will report they did not give adequate support.
- 3. The health care provider and the surgical assistant will not find the support person effective

in supporting the patient.

Objectives

Primary Aims:

- To assess a change in expected pain level from baseline, immediately after the procedure, and again ten minutes after arrival to the recovery room as determined by a 100mm visual analog scale (VAS) for patients with in-room social support during the procedure as compared to those who do not.
- To assess pre- and post-procedure state anxiety levels as determined by the 20-question State-Trait Anxiety Inventory (STAI) for patients with in-room social support as compared to patients without in-room social support.

Secondary Aims:

- To measure acceptability and effectiveness of having social support in the procedure room as reported by the surgical assistant and healthcare providers as determined by a post-procedure questionnaire.
- To evaluate if support was effectively given to the patient as reported by the support person as determined by a post-procedure questionnaire.

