1.3.11 Data Analysis

Analysis will be performed using Qualtrics statistical software. Analyses will be performed on all control and experimental group data. The control group is defined as the standard care without presence of support person, whereas the intervention group is all those receiving standard care with the presence of a support person in the procedure room. Demographic, behavioral, and clinical characteristics will be compared between the two arms using frequency tests, Student's ttest, chi-squared tests, and two-way ANOVA, where appropriate. The change in pain score, as assessed by VAS, from baseline to recovery room will be compared within each group using paired Student's t-test if the data are normally distributed or Wilcoxon signed-rank test if the data do not follow a Gaussian distribution. Similarly, the difference in the change in VAS scores between the

study arms will be compared using Student's t- or Mann-Whitney U tests, where appropriate. Questionnaire answers will be compared between both arms of the study using chi-squared statistical analysis. Statistical analysis will be performed by both the Principal Investigator and statistician.

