4.4 VISUAL ANALOG SCALE (VAS)

For these questions we are going to ask you to make an X on a line. For example, let's say you are asked how much you like Oreo cookies:

How much do you like Oreo cookies? (Make an X on the line)

very very little much

Answer the question by making an "X" on the line according to how much you like or dislike Oreo cookies. If you liked Oreo cookies a lot, then you might make an "X" on the line like so:

very / very little / much

If you liked Oreo cookies more than life itself(!), then you might make an "X" on the line like so:

very Very little Very

If you hated Oreo cookies, then you might make an "X" like so:

very very little much

If you thought Oreo cookies were just "OK," then you might make an "X" like so:

very Very little much

The idea is that if you like Oreo cookies, you make an "X" on the line closer to the phrase "very much." The closer you make the "X," the more you are saying you like Oreo cookies. If you don't like Oreo cookies, you make an "X" on the line closer to the phrase "very little." The closer you make the "X," the more you are saying you don't like Oreo cookies.

Please mark an X on the line to indicate your response to the following questions.

1. How much pain do you think you will have during procedure?	
no	worst pain
pain	in my life
ACTUAL TIME OF ASSESSMENT::	
2. How much pain you are having now (immediately at the end oprocedure)?	of the abortion
no	worst pain
pain	in my life
ACTUAL TIME OF ASSESSMENT::	
3. How much pain you are having now (in the post-abortion recent	overy room)? worst pain
	worst pain
pain	in my life
ACTUAL TIME OF ASSESSMENT:	

4.5 POST-PROCEDURE QUESTIONNAIRE FOR SUPPORT PERSON- INTERVENTIONPlease circle your answers below:

1) I had a clear understanding of my role as a support person during the procedure.
Definitely yes
Probably yes
Neutral
Probably not
Definitely not
2) I feel I provided effective support to the patient in the procedure room.
Definitely yes
Probably yes
Neutral
Probably not
Definitely not
3) I feel that the patient was comforted by my presence in the room. Definitely yes
Probably yes
Neutral
Probably not
Definitely not
4) I was comfortable in the procedure room.
Definitely yes
Probably yes
Neutral
Probably not
Definitely not
Don't know/no opinion
Last updated: 4/10/2017

5) If you felt uncomfortable in the procedure room, were you uncomfortable due to any of the following: (circle all that apply)

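### Hypotheses 2 and 3 concern how effective support was where it was given, but the only test fixed for questionnaire answers compares the arms and cannot decide them

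*Protocol*

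**What the plan says.** Protocol section 1.1.2 gives three hypotheses and three nulls. The first null is about an effect: support changes nothing in patients' pain, anxiety or satisfaction. The other two are different in kind.

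- Hypothesis 2: "The social support person will report that they were able to give effective support to the patient". Its null: "The social support person will report they did not give adequate support".
- Hypothesis 3: "The physician and the nurse will find the support person effective in supporting the patient". Its null begins: "The health care provider and the surgical assistant will not find the support person effective".

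The matching secondary aim for support persons is also a level with no comparator: "To evaluate if support was effectively given to the patient as reported by the support person as determined by a post-procedure questionnaire". The primary aims, by contrast, name a comparison with patients who had no in-room support.

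Section 1.3.11 has one sentence on the questionnaires: "Questionnaire answers will be compared between both arms of the study using chi-squared statistical analysis". The within-group tests in that section apply to pain on the VAS, where the change "from baseline to recovery room will be compared within each group using paired Student's t-test" or its rank-based alternative. The frequency tests it mentions apply to demographic, behavioural and clinical characteristics.

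**The concern.** Support persons in the control arm never enter the procedure room, so only the intervention arm can show whether support was effectively given or found effective. The planned test asks whether the arms answered alike. Those are separate questions, and the answer to one does not settle the other.

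The forms add to this. Form 4.5, item 2, for the intervention arm reads "I feel I provided effective support to the patient in the procedure room". Its control-arm counterpart in form 4.6 asks what the respondent would have provided. Forms 4.7 and 4.8 differ in the same way for staff. The comparison therefore sets reported experience against expectation. The mismatch does not depend on this, however: identical wording, or any other between-arm test of equality, would leave it in place.

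At stake is the conclusion on two of the three hypotheses. If the chi-squared p-value is used to decide them, high approval in both arms would read as a failure to show effectiveness, and a significant difference could be reported as support although most intervention-arm respondents did not find the support effective.

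**Working it through.** **Inputs.** Section 1.3.2 plans 200 participants per arm, read here as 100 patient and support-person pairs per arm. The 0.05 level is stated there for pain and is assumed here for questionnaires. The answer shares below are assumptions, because the protocol gives none. Answers are treated as independent.

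**The protocol's own figure.** Section 1.3.2 bases the larger sample for the secondary aims on 95% confidence and an interval of 10, read as ±10 percentage points. For one proportion:

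n = 1.96² × 0.25 / 0.10² = 96.04, that is 97, close to 100 per arm.

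At n = 100 and p = 0.5 the half-width is 1.96 × √(0.25/100) = 9.8 points. The sample is thus sized for estimating a proportion, an estimate that 1.3.11 does not contain. A correction for the size of the 2015 clinic population would give 81 to 94 for an assumed 500 to 5,000 patients; that count is not stated.

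**Null against null.**

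| | Nulls 2 and 3 (1.1.2) | Chi-squared (1.3.11) |
|---|---|---|
| Concerns | level where support was given | difference between arms |
| High approval in both arms | false | true |
| Low approval in both arms | true | true |
| Arms differ | depends on the intervention arm only | false |

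**Rejection rates when the arms agree.** Pearson 2×5 test, 100 per arm, simulated:

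- 90% yes in both arms (shares .70/.20/.05/.03/.02, from definitely yes to definitely not): rejects in about 4%.
- 30% yes in both arms (shares .10/.20/.20/.25/.25): rejects in about 5%.

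The test behaves alike in two situations that should give opposite verdicts on hypothesis 2. Both rates are simply its error rate when its own null is true.

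**Single data sets.** Collapsed to yes or not yes, with 100 per arm and p̄ the pooled proportion:

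X² = (p₁ − p₂)² / [2 p̄(1 − p̄)/100]

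- 95 v 95: X² = 0, p = 1.00. The exact 95% CI for the intervention arm is 88.7% to 98.4%.
- 30 v 10: X² = 0.20² / (2 × 0.20 × 0.80/100) = 0.04/0.0032 = 12.5, p = 0.0004, although 70 of 100 in the intervention arm did not say yes.
- 85 v 95: X² = 0.10² / (2 × 0.90 × 0.10/100) = 0.01/0.0018 = 5.56, p = 0.018. The result is significant and in favour of control, with 85% approval where support was given.

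**Intervention-arm analysis.** Against 50%, used only as an illustration, a rule of at least 61 yes answers out of 100 has one-sided error 0.018 and power of about 1.00 if true approval is 95%.

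**The case against.** The strongest reply is that a between-arm comparison is a declared purpose. Section 1.7 says the study will compare provider and support-person satisfaction with and without the support person in the room, and the chi-squared serves that. This stands: the test has a use, and it would be wrong to say it has no bearing on the secondary aims, the first of which also covers acceptability.

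A second reply is that 1.3.11 is a general sentence for all forms and nowhere says that its p-value decides hypotheses 2 and 3; an intervention-arm proportion could be left to an analysis plan. It is true that no decision rule is written. But the section names one analysis for these answers, and that analysis does not address two nulls the protocol itself states. This is a mismatch in what is fixed, not only missing detail.

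A reader might infer that the test rejects strongly whenever the hypotheses are false. The protocol's test does not do that: with 30% approval in both arms it rejects in only about 5%. Strong rejection needs the arms to differ.

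A reader might also want one figure for how often the test would mislead at, say, 80% against 90% approval. None is available. The rate is about 65% if the intervention arm's shares are .50/.30/.10/.05/.05, and about 29% if they are .62/.18/.10/.06/.04, each against the 90% shares above. It depends on a split between definitely and probably yes that the protocol does not give.

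Finally, a 50% cut-off appears nowhere in the protocol. That is right, and any threshold fixed in advance would remove the mismatch.

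**Conclusion.** The point holds as a mismatch between hypotheses and test. Hypotheses 2 and 3 and their nulls describe a level in the intervention arm. The one analysis fixed for questionnaire answers has a null that is compatible with near-unanimous approval and with near-unanimous disapproval, so no result from it confirms or refutes them.

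The conclusion follows from the wording and needs no numerical assumption. The rates of about 4% and 5% only illustrate it, and rest on 100 respondents per arm, assumed answer shares and independent answers. Independence is doubtful, because days are randomised and a small number of rotating providers answer repeatedly; this would widen intervals, most of all for hypothesis 3, without repairing the mismatch.

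The reach is limited to secondary aims. The pain and anxiety aims are untouched, the needed answers are already collected, and the chi-squared keeps its role for section 1.7. The change is worth making before analysis.

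**What to change.** In sections 1.1.2 and 1.3.11, state that hypotheses 2 and 3 are judged on the intervention-arm proportion answering definitely or probably yes:

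- Hypothesis 2: form 4.5, item 2.
- Hypothesis 3: form 4.7, item 2, using the physician and nurse answers. This is the nearest staff item, although it asks whether the presence was helpful rather than effective.

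Report each proportion with a 95% confidence interval that allows for procedure day and, for staff, for repeated answers by the same person. Reword nulls 2 and 3 around a threshold the sponsor fixes in advance, for example a simple majority, and conclude in favour if the lower limit exceeds it.

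Keep the between-arm chi-squared, described as a comparison of experience with expectation and not as the test of hypotheses 2 and 3.

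The cost is a few sentences and two proportions; no new data are needed. There are two downsides. A threshold must be chosen and defended, and the staff interval will be wide and rest on few clusters because few providers rotate.

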1.2 Previous similar studies

Veiga et al. (2011) evaluated the effects of social support in the post-abortion recovery room using a Medical Outcomes Survey (MOS), STAI, and a brief post-procedure questionnaire. The study found benefits to having a support person in the recovery room, with a significantly lower anxiety levels in accompanied patients. Evaluation of nurses' perspective on accompaniment found that nurses thought the patients may benefit from accompaniment, however, the study also found the nurses had concerns related to noise level, patient privacy, and space [5]. Chor et al. (2015) examined the effects of doula support in the abortion procedure room. The study found that doula support addressed patient psychological needs as those with doula support required less additional clinic supportive resources. Despite the positive psychological impact, doula support did not significantly affect patient pain or satisfaction [6].

As these are the only studies examining support in the abortion clinic, the question regarding the benefit to patients having social support in the abortion procedure room remains unanswered.

This study will also use the STAI and an adapted post-procedure questionnaire in addition to the 100mm VAS.

1.3 Design and methodology

1.3.1 Research design and General Methodological Approach

This study will be designed as a randomized, controlled trial to compare pain and anxiety levels before, during, and after in-clinic abortion in patients with and without a support person in the abortion procedure room. Each procedure day will be randomized into "support person day" ("intervention group") or "non-support person day" ("control group"). This randomization process was chosen as the most effective way to randomize without compromising patient care and study validity. Limitations to the physical space of the health center prevent patient randomization because there is no way to avoid patients knowing which arm of the study they are in: the intervention arm or the control arm.

Randomization will occur at the beginning of each procedure day by a research assistant who will pull from an opaque envelope that contains ten slips of paper, five will be marked with 'A' and the other five marked with 'B'. The half marked 'A' will indicate the procedure day will be assigned as an "intervention" day, and the other half marked 'B' will indicate the day will be assigned as a "control" day. After all ten slips of paper are pulled and ten of the procedure days have been randomized, the research assistant will replace the ten slips of paper and begin the same randomization process until the designated number of participants have been enrolled. The research assistant will initiate enrollment of patients in the study after they have consented for the abortion procedure.

All patients who present at PPSWCF's Tampa Health Center for a dilation and curettage (D&C), whether for elective pregnancy termination or management of early pregnancy complications and who are proficient enough in English to consent and understand the study procedures are eligible for participation and enrollment. Support people will be eligible for participation and enrollment if they are 18 years of age or older, are privately selected by the patient to be their support person, and who are proficient enough in English to consent and understand the study procedures. Support people for minors will be privately selected by the patient in conjunction with their parent/guardian consent.

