1.3.2 Sample Size

A total of 400 subjects will be enrolled in this study; 200 participants will enroll in the control arm and 200 will enroll in the intervention arm. Within these two arms, 100 subjects will be "patients" and "support persons." "Patients" are defined as people who will receive an in-clinic abortion on the day of their participation. "Support persons" are the individuals whom the patient chooses to accompany them during the in-clinic abortion procedure. Support persons will only actually accompany patients in the in-clinic procedure room if they are randomized to the

intervention arm of this study. Health care providers will also be invited to participate in this research study—and enrollment numbers will depend upon the amount of unduplicated staff who will perform or assist with the D&C procedure on days when enrollment will occur. "Health care providers" include the physician performing the abortion and nurses assisting the physician within the abortion procedure room.

Prior studies indicate a 20mm difference in VAS is clinically significant and that the common standard deviation for VAS scores is 23 mm [8]. Based on these assumptions, a sample size of 28 with 14 women in each arm will have 90% power to detect at least a 20mm difference between the change in pain score from baseline, to during the procedure, to after the procedure between the two groups, using a Student's t-test evaluated at the 2-sided 0.05 significance level.

We have chosen a larger sample size to also provide a representative sample of our patient population for our secondary aims of patient and support person satisfaction as well as nurse and physician satisfaction. This sample size was calculated based on the total number of in-clinic abortion patients seen in the Tampa Health Center in 2015 with a Confidence Level of 95% and a Confidence interval of 10.

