1.3.8.1 Patient Procedure and Questionnaires

- 1) After patients have consented for the D&C procedure and the study, they will complete a paper questionnaire. This questionnaire will contain demographic information and type of sedation chosen. Additionally, subjects will record their baseline level of expected pain prior to the start of the procedure. The subject will also complete the State Trait Anxiety Inventory (STAI) after the informed consent process and before the procedure starts.
- 2) On randomized intervention days, the patient will be accompanied in the procedure room by a support person.
- 3) The study physician will enter the room and perform the abortion procedure in the usual manner. The abortion procedure will remain the same on intervention days as on control days. Immediately after the procedure, the patient will complete the second 100mm VAS. Any deviations from this protocol will be recorded.
- 4) Once the patient is in the post-abortion recovery room, the patient will complete the STAI again, a post-procedure questionnaire, and the final pain level on the 100mm VAS will be recorded at least ten minutes after arrival to the recovery room. After all questionnaires have been completed and returned to research staff, the subject will be given their reimbursement gift card for participation.
- 5) The patient's complete questionnaires will be manually entered in the Qualtrics data management software which will only be managed by designated research staff. Study documents, including surveys, will be stored in a locked filing cabinet and will be accessed by research personnel only.

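### Sections 1.3.1 and 1.3.2 name pain during the procedure as a compared and powered outcome, but no VAS item records the intensity of pain experienced during it

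*Protocol*

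**What the plan says.** Two sections of the protocol describe pain as an outcome measured during the procedure. Section 1.3.1 says the trial compares "pain and anxiety levels before, during, and after in-clinic abortion". Section 1.3.2 bases its power statement on a between-arm difference in the change in pain score "from baseline, to during the procedure, to after the procedure".

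The sections that define and collect the outcome describe something else. The primary aim in Section 1.1.2 is a "change in expected pain level from baseline, immediately after the procedure, and again ten minutes after arrival to the recovery room". Section 1.3.8.1 schedules an expected-pain score beforehand, then "Immediately after the procedure, the patient will complete the second 100mm VAS", then a last score ten minutes or more into recovery. The form in Section 4.4 words the items accordingly. Item 1 asks "How much pain do you think you will have during procedure". Item 2 begins "How much pain you are having now (immediately at the end". Item 3 asks for current pain in the recovery room.

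Section 1.3.11 compares within each arm "The change in pain score, as assessed by VAS, from baseline to recovery room". It then compares the change in VAS between arms without saying at which time point.

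**The concern.** The intervention is a person present in the procedure room, and the hypothesis in Section 1.1.2 is that this lowers perceived pain. Pain felt during the procedure is the outcome closest to that mechanism, and Sections 1.3.1 and 1.3.2 say it is compared and powered. If no item records it, the trial cannot deliver the outcome those sections promise, and a later analysis plan cannot supply it.

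Two things are at stake. First, a conclusion about pain during the procedure would rest on scores of pain after it. Second, the one interval that Section 1.3.11 names subtracts an expectation about the procedure from current pain in recovery. A drop within an arm could then be reported as relief when it may show only that recovery hurts less than the procedure was expected to hurt.

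**Working it through.** **1. The plan's own figure.** Section 1.3.2 gives 14 women per arm for 90% power, with a 20 mm difference, SD 23 mm and two-sided 0.05. Normal approximation: n per arm = 2 × (1.960 + 1.282)² × 23² / 20² = 2 × 10.51 × 529 / 400 ≈ 27.8, so 28 per arm (exact t: 28.8, so 29). The stated total of 28 therefore matches the per-arm number. With 14 per arm, power is about 63% (normal) or 60% (t). That is a separate matter with little consequence at the planned enrolment, read as 100 patients per arm. It matters here only because the statement is attached to a score *during the procedure*.

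**2. Which pain scores are claimed and which are collected.**

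| Section | Before | During | Immediately after | Recovery |
|---|---|---|---|---|
| 1.3.1 (design) | yes | **yes** | after, unspecified | after, unspecified |
| 1.3.2 (power) | yes | **yes** | after, unspecified | after, unspecified |
| 1.1.2 (primary aim) | yes, expected pain | no | yes | yes |
| 1.3.8.1 (procedures) | yes, expected pain | no | yes | yes |
| 4.4 (VAS form) | yes, expected pain | no | yes, current pain | yes, current pain |
| 1.3.11 (within-arm test) | yes | no | not named | yes |
| 1.3.11 (between-arm test) | change score | no time point | no time point | no time point |

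None of the three VAS items records experienced pain during the procedure. Item 1 refers to the procedure but is a forecast made before it. Item 2 follows the procedure and asks about the present moment.

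**3. Other patient items.** The post-procedure questionnaires in Sections 4.2 and 4.3 ask both arms, on a five-category scale, whether the discomfort felt in the procedure was acceptable. That concerns the right period but rates acceptability, not intensity.

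**4. What the named change score means.** Let E be expected procedural pain (item 1), R current pain in recovery (item 3), and P the pain actually felt during the procedure (not collected). Then

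R − E = (R − P) + (P − E).

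The first term is how far pain has subsided since the procedure. The second is how wrong the expectation was. Without P the two cannot be separated, so a negative R − E within an arm is not a measure of relief.

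**5. Between arms.** The arm difference in mean (R − E) equals the arm difference in mean R minus the arm difference in mean E. If expectations are balanced, this is a valid comparison of recovery pain. It is still not a comparison of pain during the procedure.

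**The case against.** The strongest reply is that the primary aim, the schedule and the form agree with one another. They name the same three assessments, and against that aim nothing is missing. *During* in Sections 1.3.1 and 1.3.2 may be shorthand for the middle score. Section 1.3.1 also claims anxiety during the procedure, although the STAI is given only before and after, which points to loose wording more than to a lost measurement. This reading is plausible. If it is right, the design and power statements still name an outcome the trial does not have and need rewording.

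A reader might infer that the trial says nothing about pain in the period when the support person acts. The documents do not support that. Item 2 is scored immediately at the end, before the recovery-room steps in Section 1.3.8.1, and is a close proxy; the acceptability item also touches on the procedure.

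A reader might also infer that recovery pain is the only pain score tested. The documents do not fix that. Section 1.3.11 has a second, between-arm test with no stated time point. Its opening word, *Similarly*, suggests the recovery interval carries over but does not say so, and an SAP that is not shown may settle it.

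Finally, the mismatch between expectation and recovery pain affects the reading of the within-arm change. It does not by itself invalidate the between-arm contrast, which takes the same difference in both arms. That stands.

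**Conclusion.** The point holds as an inconsistency between the stated outcome and the instrument. Sections 1.3.1 and 1.3.2 name pain during the procedure; none of the three VAS items measures its intensity, and the only other patient item on the procedure itself rates acceptability. Section 1.3.11 names one interval, baseline to recovery, for the within-arm test, although the primary aim also lists the immediate post-procedure score. A within-arm fall over that interval cannot be read as pain relief.

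This conclusion rests on the protocol text alone and needs no numerical assumption. A reader might wish to turn it into a loss of power. That would require knowing how much of an effect on procedural pain remains when pain is scored afterwards, and how strongly patients treated on the same day resemble one another. The protocol gives neither, so no power figure is attached.

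**What to change.** Preferred: at the immediate post-procedure VAS, ask *How much pain did you have during the procedure?*, either in place of the current-pain item or beside it. The score then refers to the same period as the baseline expectation. In Section 1.3.11, state that the between-arm pain comparison includes this immediate post-procedure score, adjusted for baseline expected pain, as well as the recovery score. Do not present the within-arm change from expectation to recovery as relief.

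The cost is one form item and one analysis sentence. It has to be done before data collection. The downside is that the item relies on short recall, which sedation may affect; the protocol already records sedation, so this can be examined. The adjustment also presumes that expected pain is not itself moved by knowing the arm. Section 1.3.12 concedes that control patients may be more anxious at baseline for such a reason, so the unadjusted comparison should be shown too.

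Alternative: keep the form as it is, remove *during* from the pain statements in Sections 1.3.1 and 1.3.2, restate the powered endpoint as pain immediately after the procedure and in recovery, and limit the conclusion to that. This costs only wording, but gives up any claim about the intensity of pain during the procedure.
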